### 3 STATISTICAL ANALYSES

#### 3.1 GENERAL CONSIDERATIONS

In general, continuous data will be summarized using the number of observations available, mean, standard deviation (SD), median, minimum, and maximum. Categorical and ordinal data will be summarized using the count and percentage of participants. The summary statistics will be provided at each visit, including data collected beyond Week 24.

The baseline value of efficacy parameters is defined as the last available value up to randomization date and prior to the first dose of study medication unless otherwise specified. The baseline value of the other parameters is defined as the last available value prior to the first dose of investigational medicinal product (IMP) if the participant is treated, or the last available value up to randomization date if the participant is not exposed to IMP.

For endpoints collected on the daily CRSsNP sinonasal symptom diary, baseline is defined as the average of the scores in the 7 days prior to randomization. If there are less than 7 but at least 4 non-missing scores available, the baseline score is the average of the available scores in the 7 days. If there are less than 4 non-missing scores, then baseline will be the average of the most recent 4 days with non-missing scores prior to randomization.

Stratification factors used in analyses will be derived based on eCRF data (for background INCS and region) or central laboratory data (for screening blood eosinophil count).

Unless otherwise specified, analyses will be performed by intervention group and overall for baseline and demographics characteristics.

#### *Observation period*

The observation period will be divided into 4 segments:

- The **pre-treatment period** is defined as the period up to the first IMP administration.
- The **treatment-emergent (TE) period** is defined as the period from the first IMP administration to the last IMP administration + 98 days. The treatment-emergent period includes the following 2 periods:
  - The **on-treatment period** is defined as the period from the first IMP administration to the last administration of the IMP + 14 days
  - The **residual treatment period** is defined as the period from the end of the on-treatment period to the end of the treatment-emergent period.
- The **post-treatment period** is defined as the period after the end of the treatment-emergent period.

The on-study observation period is defined as the time from the first IMP until the end of the study defined as the last scheduled visit for those who completed the study and the end-of-study date

collected on electronic case report form (e-CRF) page “Completion of End of Study/Follow-up” for those who did not complete the study. If death is the end-of-study reason, date of death will be used.

## 3.2 PRIMARY ENDPOINT ANALYSIS

### 3.2.1 Definition of endpoint

The primary endpoint is the change from baseline to Week 24 in LMK score in the dupilumab group. The LMK score is based on assessment of the CT scan findings for each sinus area (maxillary, anterior ethmoid, posterior ethmoid, sphenoid, and frontal sinus on each side). The extent of mucosal opacification is rated on a 3-point scale ranging from 0 = normal to 2 = total opacification. In addition, the ostiomeatal complex is graded as 0 = not occluded or 2 = occluded. The maximum score is therefore 12 per side for a maximum total score of 24, corresponding to the sum of all sinuses and the ostiomeatal unit.

### 3.2.2 Main analytical approach

The primary endpoint will be analyzed on the ITT with screening blood eosinophil count  $\geq 300$  cells/mm^3 population in the dupilumab group. Intercurrent events (IE) handling strategies are described below:

- The following IE will be handled with the composite strategy:
  - Undergoing sinonasal surgery for CRSsNP or taking SCS for any reason prior to Week 24: data after surgery (actual date) or SCS use will be excluded from the analysis and the worst post-baseline value on or before the time of surgery or SCS use will be used to assign the Week 24 value (ie, WOCF approach). For participants with no post-baseline values, the baseline value will be used.
- The following IEs will be handled with the treatment policy strategy (without IE that need to be handled with composite strategy). Data collected after starting such IEs will be included.
  - Taking other prohibited/rescue medications.
  - Discontinuing the study intervention.

No missing data will be imputed. Descriptive statistics (number of participants, mean, SD, median, minimum and maximum) and 95% CI of the mean (based on the t distribution) in the dupilumab group will be provided.

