	Deleted the phrase "2-part" from the study title.	Due to protocol change, the Part B Phase 3 study will no longer be conducted. Part A is modified and remains a Phase 2 study.
	Updated study Phase from 2/3 to 2	
	Minor editorial and typographical changes wherever applicable	Formatting and typographical
	Updated patient to participant wherever applicable	Formatting and typographical
1.1 Synopsis	
Deleted note with below text: The primary analysis of Part A at Week 24 (details in Section 9.6) will be conducted both to provide initial evidence of efficacy of dupilumab in adult participants with severe or uncontrolled CRSsNP and inform the initiation and design of Part B.
 
Added new note with below text: Modification of the treatment period will result in all patients who complete the treatment period being treated for a minimum of 24 weeks and a maximum of 52 weeks, or until the last patient randomized completes a minimum treatment period of 24 weeks.
	Since the purpose of the study has now changed from Phase 2/3 to a Phase 2 and there is no longer need to assess efficacy beyond 24 weeks, the 52-week treatment period for all participants in Part A is now variable between 24 weeks and 52 weeks. A minimum of 24-week treatment period for all participants allows for reliable assessment of the LMK endpoint in participants with CRSsNP.
1.1 Synopsis 3 Objectives and Endpoints	
Updated the primary objective and endpoint from: Primary Objective To evaluate the efficacy of dupilumab as assessed by the reduction at Week 24 in sinus opacification on computerized tomography (CT) scan and sinus total symptom score (sTSS) compared to placebo
 
To: To evaluate the efficacy of dupilumab as assessed by the reduction at Week 24 in sinus opacification on computerized tomography (CT) scan in the dupilumab group only
	Because the reduction in sample size does not support reasonable power for the symptoms score sTSS and for placebo comparison.

Section # and Name	Description of Change	Brief Rationale

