5.4 Screen Failures	Added the below sentence: All other screening procedures must be repeated for rescreening.	To clarify to participating clinical sites that in case of rescreening all procedures need to be repeated, except CT scan if within the defined window period.
6.1 Study Intervention(s) Administered	Addition of the following sentence: 'During study visits, the IMP is administered on sites after all procedures.'	In order to further clarify that IMP will be administered at sites at the time of Visits.
6.5.3 Rescue medicine	Changed from Short course OCS (prednisone or equivalent prednisolone up to 7 days; avoid use 4 weeks before Week 24 or Week 52, where applicable). To Short course OCS (prednisone or equivalent prednisolone up to 14 days; avoid use 4 weeks before Week 24 or Week 52, where applicable).	To clarify an inconsistency between Prohibited medications and Rescue medications, the short course of OCS is up to 14 days.

Section # and Name	Description of Change	Brief Rationale
8.6 Pharmacodynamics	Removed measurement of secreted P-glycoprotein.	Test is unable to be performed by the Sponsor due to assay limitations.
9.2 Sample size determination 9.3 Populations for analyses	Sample size determination updated. Primary population changed from ITT population to ITT population with screening blood eosinophil count $\geq 300$ cells/mm  .	To reflect changes in the study primary objective and endpoint.
9.1 Statistical hypotheses 9.4.1 General considerations 9.4.2 Primary endpoint(s)	Statistical hypotheses removed. Multiplicity consideration removed. Multiple imputation removed. Model-based analyses removed. Sensitivity and subgroup analyses removed. Use of descriptive statistics for all endpoints.	To apply more appropriate analysis methods based on the reduced sample size.
9.4.2 Primary endpoint(s)	The intercurrent events handling strategy for taking SCS for any reason prior to Week 24 was changed from 'all data collected after SCS use will be used in the analysis' to 'data after the IE will be set to missing and the worst post-baseline value on or before the time of the IE will be used to impute missing Week 24 value (WOCF)'.	To change handling of taking SCS for any reason in the primary estimand to an approach more appropriate for this clinical setting.

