### 3 OBJECTIVES AND ENDPOINTS

**Table 1 - Objectives and endpoints**

Objectives	Endpoints
Primary	

 
• To evaluate the efficacy of dupilumab as assessed by the reduction at Week 24 in sinus opacification on computerized tomography (CT) scan in the dupilumab group only
 
	
 
• Change from baseline to Week 24 in opacification of sinuses assessed by CT scan using the Lund-Mackay (LMK) score in the dupilumab group
 

Secondary	

 
• To evaluate the efficacy of dupilumab as assessed by the reduction at Week 24 in sinus opacification on CT scan and sinus total symptom score (sTSS) compared to placebo
 
	
 
• Change from baseline to Week 24 in opacification of sinuses assessed by CT scan using the LMK score
 
• Change from baseline to Week 24 in sTSS*
 

 
• To evaluate the safety and tolerability of dupilumab in CRSsNP patients compared to placebo
 
	
 
• Incidence of treatment-emergent adverse events (TEAEs), of treatment-emergent serious AEs (TESAEs), and TEAEs leading to treatment discontinuation, abnormal laboratory values, and vital signs
 

 
• To evaluate the pharmacokinetics (PK) of dupilumab in CRSsNP patients compared to placebo
 
	
 
• Dupilumab concentration in serum
 

 
• Assessment of immunogenicity to dupilumab over time compared to placebo
 
	
 
• Assessment of immunogenicity to dupilumab as determined by the incidence, titer, and neutralizing antibody (NAb) status of treatment-emergent anti-drug antibody (ADA) response over time compared to placebo
 

Exploratory	

 
• [REDACTED]
 
	
 
• [REDACTED]
 

 
• [REDACTED]
 
	
 
• [REDACTED]
 

 
• [REDACTED]
 
	
 
• [REDACTED]
 

 
• [REDACTED]
 
	
 
• [REDACTED]
 

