### 4.2 SCIENTIFIC RATIONALE FOR STUDY DESIGN

EFC16723 is designed as a double-blind, randomized, placebo-controlled, study to minimize bias in data collection and interpretation. The presence of a placebo arm is appropriate for the objectives of this study since it will provide the most robust assessment of the efficacy and safety

of dupilumab. The study has a 24 to 52 -week study treatment period to provide initial evidence related to the treatment effect of dupilumab in patients with Type-2 inflammation (as indicated by peripheral blood eosinophil counts  $\geq 300$  cells/mm $^3$ ) CRSsNP and to provide safety information. In addition, a post-hoc analysis to assess the efficacy of dupilumab on upper airway symptoms as measured by SNOT-22 in the subset of asthma patients with CRS from the dupilumab Phase 3 asthma study EFC13579 (QUEST) was performed. Clinically meaningful improvement from baseline in SNOT-22 was observed only in patients who had peripheral blood eosinophil counts  $\geq 300$  cells/mm $^3$  and not in those with  $< 300$  cells/mm $^3$ . In the study, to further evaluate the predictive value of baseline peripheral blood eosinophil counts as a potential marker of treatment response to dupilumab, a subset of participants with blood eosinophil counts of  $< 300$  cells/mm $^3$  will be randomized while the primary analysis population will remain as participants who have peripheral blood eosinophil counts  $\geq 300$  cells/mm $^3$ .

The 24-week treatment duration should be sufficient for the demonstration of the efficacy with dupilumab based on the efficacy results seen in CRSwNP. This duration is also sufficient for safety assessment given the extensive safety experience with dupilumab including in the related condition of CRSwNP.

Rescue medications and/or surgery for CRSsNP deemed necessary by Investigators will be allowed, which mirror the expected future therapeutic paradigm of dupilumab in this population in clinical practice.

The primary efficacy assessment will be change from baseline in the LMK at Week 24 in the dupilumab group. Other supportive assessments, including sTSS scores for the main symptoms in CRSsNP (nasal congestion [NC]/obstruction, loss of sense of smell, rhinorrhea, facial pain/pressure), VAS for rhinosinusitis severity, and SNOT-22 will also be collected, to provide additional evidence of therapeutic benefit.

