#### Type of participant and disease characteristics

I 02. Participants must have bilateral inflammation of paranasal sinuses in CT scan with LMK  $\geq 8$  and bilateral ethmoid opacification before randomization.

I 03. Participants must have ongoing symptoms of loss of smell and rhinorrhea (anterior/posterior) of any severity, with or without facial pain/pressure for at least 12 consecutive weeks by Visit 1.

I 04. Participants must have ongoing symptoms of NC/obstruction at least 12 consecutive weeks before Visit 1 and a NC score of  $\geq 2$  at Visit 1 (day score) and Visit 2 (weekly average score).

I 05. Participants must have sTSS (NC, rhinorrhea, facial pain/pressure)  $\geq 5$  at Visit 1 (day score) and Visit 2 (weekly average score).

I 06. Participants must have at least one of the 2 following features:

- a) Prior sinonasal surgery (see note at end of section 5.2 for definitions of sinonasal surgery) for CRS,
- b) Treatment with SCS therapy for CRS as defined by any dose and duration within the prior 2 years before screening (Visit 1) or intolerance/contraindication to SCS.

I 07. No restrictions on eosinophil count.

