## 8.1 EFFICACY ASSESSMENTS

### 8.1.1 Computerized Tomography Scans using Lund-Mackay

Computerized tomography scans using the LMK allows the assessment of sinus opacification ([37](#)).

The CT scan LMK staging system represents the most widely established method of sinus CT scoring in clinical trials. The LMK total score is based on assessment of the CT scan findings for each sinus area (maxillary, anterior ethmoid, posterior ethmoid, sphenoid, and frontal sinus on each side). The extent of mucosal opacification is rated on a 3-point scale ranging from 0 = normal to 2 = total opacification. In addition, the ostiomeatal complex is graded as 0 = not occluded or 2 = occluded. The maximum score is therefore 12 per side for a maximum total score of 24, corresponding to the sum of all sinuses and the ostiomeatal unit.

This scoring system has been validated in several studies ([37, 38, 39](#)).

The CT scans should be performed anytime during the screening period before first administration of IMP at Visit 2 (baseline CT data), Visit 5 (Week 24). The Visit 7 (Week 52) CT scan is optional due to variable treatment period. Whenever possible a cone beam CT scan should be utilized. In countries for which a specific approval procedure for the CT scan is required by a different committee than the local IEC/IRB, a 4-month window is required between 2 CT scans. If a participant needs to be rescreened or is terminated early from the study intervention, the repeated CT scan or following CT scan must be done over a 4-month restriction window. If Participant who discontinue the study intervention prematurely, the CT scan will be performed as soon as possible, with all other assessments normally planned in EOT Visit as long as between 2 CT scans can meet a 4-month restriction window. Otherwise, the CT scan can be done in next scheduled visit.

It is recommended to avoid use of OCS as rescue therapy during the Week 20 to Week 24 or-the Week 48 to Week 52. If a participant must use OCS during this period to control CRSsNP worsening/acute sinusitis based on Investigator judgment the site should make every efforts to schedule the Week 24 CT scan or the Week 52 CT scan-prior to OCS rescue therapy.

The CT scan will be performed locally and reviewed centrally in a pre-specified manner as described in the Image Acquisition Standards (IAS) and Image Interpretation Standards (IIS) (refer [Section 1.3](#)).

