### 1.2 OBJECTIVES AND ENDPOINTS

Table 1 - Objectives and endpoints

Objectives	Endpoints
Primary	
To evaluate the efficacy of dupilumab as assessed by the reduction at Week 24 in sinus opacification on computerized tomography (CT) scan in the dupilumab group only	

• Change from baseline to Week 24 in opacification of sinuses assessed by CT scan using the Lund-Mackay (LMK) score in the dupilumab group

Secondary	
To evaluate the efficacy of dupilumab as assessed by the reduction at Week 24 in sinus opacification on CT scan and sinus total symptom score (sTSS) compared to placebo	

• Change from baseline to Week 24 in opacification of sinuses assessed by CT scan using the LMK score

• Change from baseline to Week 24 in sTSS*

*\*Composite severity score consisting of nasal congestion, anterior/posterior rhinorrhea, facial*

Objectives	Endpoints
	pain/pressure items of the CRSsNP sinonasal symptom e-diary

 
• To evaluate the safety and tolerability of dupilumab in CRSsNP patients compared to placebo
 
	
 
• Incidence of treatment-emergent adverse events (TEAEs), of treatment-emergent serious AEs (TESAEs), and TEAEs leading to treatment discontinuation, abnormal laboratory values, and vital signs
 

 
• To evaluate the pharmacokinetics (PK) of dupilumab in CRSsNP patients
 
	
 
• Dupilumab concentration in serum
 

 
• Assessment of immunogenicity to dupilumab over time
 
	
 
• Assessment of immunogenicity to dupilumab as determined by the incidence, titer, and neutralizing antibody (NAb) status of treatment-emergent anti-drug antibody (ADA) response over time
 

Exploratory	

 
• [REDACTED]
 
	

 
• [REDACTED]
 
	

 
• [REDACTED]
 
	

 
• [REDACTED]
 
	

 
• [REDACTED]
 
	

 
• [REDACTED]
 
	

 
• [REDACTED]
 
	

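### The primary LMK result is a one-arm change, not a treatment effect, and the placebo difference that does estimate the effect is planned without baseline adjustment

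*SAP*

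**What the plan says.** SAP 1.2 words the primary objective as "efficacy of dupilumab as assessed by the reduction at Week 24 in sinus opacification on computerized tomography (CT) scan in the dupilumab group only"; Protocol Table 1 has the same objective. SAP 3.2.2 summarises it with descriptive statistics and adds that "95% CI of the mean (based on the t distribution) in the dupilumab group will be provided". The population is the ITT set with screening eosinophils of at least 300 cells/mm³.

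On entry, Protocol 5.1 (I 02) says "Participants must have bilateral inflammation of paranasal sinuses in CT scan with LMK" of at least 8. Protocol 8.1.1 takes the screening-period scan as the baseline scan.

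The placebo comparison is kept as secondary. Protocol 9.4.3 analyses the secondary endpoints in the same way as the primary and adds a 95% CI for the treatment difference. SAP 3.3.2 gives the mean LMK and sTSS differences with t-based intervals and names no covariate.

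The reasons are disclosed in the Amendment 02 summary. On the one-arm primary: "Because the reduction in sample size does not support reasonable power for the symptoms score sTSS and for placebo comparison". On removing models: "To apply more appropriate analysis methods based on the reduced sample size". Protocol 9.1 says that no hypotheses will be tested. Protocol 4.2 says that "a placebo arm is appropriate for the objectives of this study since it will provide the most robust assessment of the efficacy and safety", and the same section names the dupilumab-group LMK change as the primary efficacy assessment.

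**The concern.** The objective uses the word efficacy, but its estimate comes from one arm. Participants are selected for a high score on the scan that becomes their baseline, so some fall in LMK is possible without any drug effect. A reader who sees a dupilumab interval wholly below zero under an efficacy objective could take it as evidence that the drug works. Neither SAP 3.2.2 nor Protocol 9.4.2 says that the interval describes within-group change.

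The difference from placebo removes what is common to both arms. At about 14 per arm, though, mean baseline scores can differ by chance. If change depends on baseline, an unadjusted difference in change scores carries part of that imbalance. What is at stake is how the headline result is read, and how well the one randomised estimate is protected from baseline imbalance.

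**Working it through.** **Inputs.** SAP 4 and Protocol 9.2: SD 5, dropout 10%, 15 per arm (SAP 4), so n = 15 × 0.9 = 13.5 evaluable. Assumed, because the documents do not give them: SD 5 in the placebo arm too, and r, the correlation of baseline LMK with LMK change.

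**1. The plan's own figure.** Half-width = t(n−1) × SD/√n = 2.169 × 5/√13.5 = 2.95. The stated value of approximately less than 3 is reproduced (3.02 at n = 13, 2.89 at n = 14).

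**2. Unadjusted placebo difference.** t(2n−2) × SD × √(2/n) = 2.060 × 5 × √(2/13.5) = 3.96, which is 1.34 times the one-arm figure.

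**3. Baseline-adjusted difference.** t(2n−3) × SD × √(1−r²) × √(2/n) × √(1+1/(2n−4)), where the last factor is the average cost of baseline imbalance:

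| r | Half-width | Ratio to unadjusted |
|---|---|---|
| 0 | 4.06 | 1.02 |
| 0.3 | 3.87 | 0.98 |
| 0.5 | 3.51 | 0.89 |

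The two intervals are equally wide, on average, at |r| = 0.21. The ratios apply equally to sTSS, for which no SD is given.

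**4. The cost in a single trial.** The 0.1 point lost at r = 0 is an average. In simulation at r = 0, SD 5 and 14 per arm, the mean cost is about 0.09, about 39% of trials lose more than 0.1, and 5% lose about 0.33 or more.

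**5. What imbalance can do to the unadjusted difference.** With an assumed baseline SD of 3 to 5 and 14 per arm, the 95% range of chance imbalance in mean baseline LMK is 1.96 × SD × √(2/14), or ±2.2 to ±3.7 points. The slope of change on baseline is r × 5/baseline SD, so the shift at the edge of that range is 1.96 × |r| × 5 × √(2/14) = 3.70 × |r|; the baseline SD cancels. That is 0.74 point at |r| = 0.2 and 1.11 at 0.3.

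**6. Non-drug change in the one-arm result (illustrations only).** The documents give no source mean, LMK reliability or placebo change.
- Regression to the mean, with between-person SD 4 and within-person SD 2 to 3: −0.71 to −1.43 points at a source mean of 8, and −0.08 to −0.21 at 16 with scores capped at 24. A source mean of 6 with between-person SD 3 gives up to −2.4. These values do not bound the effect.
- If the drug adds nothing and both arms fall by 1, 2, 3 or 4 points (SD 5, 14 evaluable), the dupilumab interval lies wholly below zero with probability 10%, 28%, 55% or 79%.

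**The case against.** The strongest reply is that this is already handled. The one-arm primary is disclosed, no test or success rule attaches to its interval, and a separate secondary objective covers LMK and sTSS against placebo with a 95% CI. All of that stands. A reader might infer that every efficacy conclusion must rest on the placebo difference. The documents do not support that: Protocol 4.2 praises the placebo arm but also names the dupilumab-group change as the primary efficacy assessment, so such a rule would reorder the protocol's hierarchy through the SAP.

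On the covariate, the unadjusted difference is valid under randomisation. Regression to the mean from the entry threshold acts on both arms alike, so it is no argument for adjustment. SAP 5.3 tabulates baseline LMK by group, so imbalance will be visible. The precision gain may be nil: the regression model in step 6, with between-person SD 4, source means of 8 to 16 and change SD 5, implies |r| of about 0.11 to 0.28, on both sides of the break-even at 0.21. These points stand as well. They leave chance imbalance, which a table shows but does not correct, as the main reason for the covariate. They also argue for adding the adjusted estimate beside the planned one, not for replacing it.

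**Conclusion.** The point holds as a gap in interpretation and a modest, cheap improvement, not as an error. The sample-size figure is arithmetically sound and the planned difference is valid. The primary interval describes change within the dupilumab group; the plan's estimate of treatment effect is the randomised difference, whose half-width is about 4.0 LMK points against about 3 for the one-arm mean (SD 5 in both arms, 13.5 evaluable). One baseline covariate costs about 0.1 point of half-width on average if baseline is unrelated to change, and more in a trial with large imbalance. It narrows the interval on average only if |r| exceeds about 0.21, and r is unknown.

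Two stronger readings should be resisted. One is that the trial has no controlled efficacy estimate; it has one, as a secondary endpoint. The other is that a dupilumab interval below zero is a planned success criterion; Protocol 9.1 rules out hypothesis testing and no such criterion is stated. How much of the one-arm change is unrelated to the drug cannot be computed from the documents.

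**What to change.** Keep the primary objective, the estimand and the endpoint hierarchy.

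1. **SAP 3.3.2**, beside the planned unadjusted difference, add: *For LMK and for sTSS, the dupilumab–placebo difference in Week 24 change will also be estimated from a linear model containing treatment and the baseline score, with its 95% CI and with intercurrent events treated as in the primary analysis.*
2. **SAP 3.9**, record this model as an addition to the descriptive approach in Protocol 9.4.3, which does not provide for it.
3. **SAP 3.2.2**, add: *This interval describes change within the dupilumab group. The estimate of treatment effect is the difference from placebo in Section 3.3.2.*

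The cost is SAP text and one extra model per endpoint, using baseline scores already collected; no new participants or data are needed. The statistical price is one degree of freedom, with the loss of width given above. The additions should be final before unblinding.
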